27.0 STUDY-SPECIFIC APPENDICES

Appendix A
REVISION HISTORY

The purpose of this appendix is to describe modifications made to this document, in detail, when moving from Version 1.0 to Version 2.0.

| Overall summary of changes | | |
|---|---|---|
| Version 2.0: Exclusion Criteria EC-3 and EC-7 | | |
| Section modified | Original text | Updated text |
| 1.0 Synopsis- Selection of Subjects-EC-3 7.2-1 Exclusion Criteria EC-3 | The patient is assessed by the investigator as being at high risk of infection, or known to be immune-deficient, based on the environment, duration and site conditions of catheterization. | The patient is assessed by the investigator as being at high risk of CLABSI, or known to be CLABSI, based on the environment, duration, and site conditions of catheterization. |
| 1.0 Synopsis- Selection of Subjects-EC-7 7.2-1 Exclusion Criteria EC-7 | The patient is clinically diagnosed with sepsis or bacteremia. | The patient is assessed by the investigator as being at high risk of blood stream infection, or known to be sepsis, caused by blood stream infection. |
| | | |
| | | |
| | | |
| | | |

Appendix B

Evaluation Criteria

CLABSI/CRBSI evaluation criteria

CLABSIs: Primary bloodstream infections in hospitalized patients occur during the use or within 48 hours after removal of indwelling central venous catheters and are unrelated to the presence of infections at other sites. CRBSI: Catheter-induced bloodstream infections are primary infections that occur in patients with a central venous catheter and where there is laboratory evidence that the catheter is the source of the bloodstream infection.

Patients who develop infection symptoms such as fever, chills, and/or hypotension after catheterization and at least one peripheral venous blood culture positive of bacteremia or fungemia without any other obvious sources of bloodstream infection show one of the following: semi-quantitative catheter-tip culture ≥ 15 cfu, while the same microorganism (species) is isolated from both the catheter-tip culture and the peripheral blood culture; the ratio of bacterial growth (cfu/ml) between quantitative catheter-tip and peripheral blood cultures, which are performed concurrently, is greater than 3:1; the positive alarm time of the blood specimen is more than 2 hours earlier than that of the peripheral equivalent specimen.

Diagnostic criteria

a. Retain the catheter:

If two sets of blood cultures are positive and present the same species

- In the absence of evidence of other infections, it indicates possible CRBSI;
- If the same pathogen is found in both sets of cultures and the blood culture from the catheter reports positive 120 minutes earlier than the one from the peripheral vein: It indicates CRBSI if there is no evidence of other infections (it may also indicate CRBSI if the difference in time to positivity between the two sets of blood cultures is less than 120 minutes but have the same identification and drug sensitivity results).
- If both sets of blood cultures are positive, and the bacterial count from catheter blood cultures is at least five times higher than that of peripheral venous blood cultures,

it indicates possible CRBSI (for manual quantitative blood culture systems) if there is no evidence of other infections.

If only the catheter blood culture tests positive: It will not be a conclusive evidence of CRBSI, but may be due to bacterial colonization or contamination during blood specimen collection.

If only the peripheral venous blood culture tests positive: It will not be a conclusive evidence of CRBSI; however, if it is *Staphylococcus aureus* or *Candida*, in the absence of other evidence of infection, it indicates possible CRBSI.

If both sets of blood cultures are negative: It indicates no CRBSI.

The reference table is as follows:

| Catheter | Peripheral vein | Conditions | Judgment of results |
|----------|-----------------|--|----------------------|
| + | + | | Possible CRBSI |
| + | + | The catheter-tip culture reports positive 120 minutes earlier than the peripheral vein culture | Indicating CRBSI |
| | | Catheter bacterial concentration is 5 times higher than peripheral vein | |
| + | - | | Cannot be determined |
| - | + | | Cannot be determined |
| | | In the case of Staphylococcus aureus , or Candida | Indicating CRBSI |
| - | - | | Not CRBSI |

b. Removal of catheters:

If one or more sets of blood cultures are positive and the catheter-tip culture is positive: The detection and drug-sensitivity spectrum analysis indicate the same species in both types of cultures: It indicates possible CRBSI;

If one or more sets of blood cultures are positive and the catheter-tip culture is negative: If the cultures are positive for Staphylococcus aureus or Candida and there is no evidence of other infections, it indicates possible CRBSI and may require additional positive blood cultures of the same organism to reach a conclusion;

If the blood culture is negative and the catheter-tip culture is positive: It indicates catheter colonization, not CRBSI;

If both sets of blood cultures and end-of-catheter cultures are negative: It indicates no CRBSI.

The reference table is as follows:

| Catheter tip | Peripheral vein 1 | Peripheral vein 2 | Judgment of results |
|--------------|-------------------|-------------------|--|
| + | + | + | Possible CRBSI |
| + | + | - | |
| - | + | - | Cultures are positive for Staphylococcus aureus or Candida and there is no evidence of other infections, it indicates possible CRBSI |
| - | + | + | |
| + | - | - | Catheter-colonizing bacteria |
| - | - | - | Not CRBSI |

Lift Scale

| Score | Description of Sample Lift |
|-------|----------------------------|
| 0 | No lift |
| 1 | 1 - 25% |
| 2 | 26 - 50% |
| 3 | 51 - 75% |
| 4 | 76 - 99% |

| | |
|---|---------|
| 5 | Missing |
|---|---------|

Skin Irritation Scale- Erythema

| Score | Description of Response |
|-------|---|
| 0 | No Erythema |
| 1 | Very slight erythema (barely perceptible- edges not well defined) |
| 2 | Well-defined erythema (pale red in color and area definable) |
| 3 | Moderate erythema (definite red in color and rea definable) |
| 4 | Severe erythema (beet or crimson in color) |

Skin Irritation Scale- Edema

| Score | Description of Response |
|-------|--|
| 0 | No Edema |
| 1 | Very slight edema (barely perceptible edges not well defined) |
| 2 | Well-defined edema (area definable but not raised more than 1 mm) |
| 3 | Moderate edema (area well definable and raised approximately 1 mm) |
| 4 | Severe edema (area raised more than 1 mm and extending beyond exposure area) |

Itch

| Score | Description of Response |
|-------|--|
| 0 | No itching |
| 1 | Slight itching |
| 2 | Moderate itching |
| 3 | Extreme itching: could not stop scratching at any time/ need a treatment |

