1.0 SYNOPSIS

| | |
|---|--|
| Study Title | A Randomized Perspective, Open and Parallel Controlled Study Comparing 3M Tegaderm CHG I.V. Securement Dressing with 3M Tegaderm Transparent Dressing for Evaluation of Antimicrobial Efficacy on DVC Insertion Site in Adult in Critical Care |
| Study Type | post-market |
| Principal Investigator (PI) | Name: [name] Title: [name]: Ruijin Hospital Critical Care Department |
| Device under Investigation Summary | 3M Tegaderm CHG I.V. Securement Dressings This product is composed of a transparent dressing and a gel pad. The gel pad contains 2% (w/w) chlorhexidine gluconate (CHG), which is an antimicrobial agent. This product is suitable for covering and protecting catheter sites (including arterial and venous catheters, intravascular catheters, and percutaneous devices) on the body surface and securing devices to healthy skin. This product should not be used on infected wounds or unhealthy skins. |
| Sponsor | 3M China |
| Purpose | The objective of this study is to evaluate the antimicrobial efficacy of Tegaderm CHG dressing on DVC insertion site in adult patients in critical care |
| Design | This is a single-center, prospective, randomized controlled clinical trial designed to compare the antimicrobial efficacy of Tegaderm CHG I.V. Securement Dressing and transparent dressings for deep vein catheterization in adult ICU patients. Considering the easy-to-distinguish appearances of both products used, this trial will adopt an open-label design. The primary endpoint is the rate of CVC tip colonization (positive catheters after culture/total catheters). Subjects eligible for enrollment will be randomly assigned to either the Tegaderm CHG dressing group or the transparent dressing group, and patients in both groups will be given catheterization according to the hospital's standards and nursed according to the catheter maintenance procedure. The investigator would monitor the subjects during dressing changes, observing the subjects' general conditions, skin condition at the DVC site and the dressing condition, and change a dressing or take relevant measures (if |

| | |
|------------------------------|--|
| | applicable), until the end of the trial, i.e. CVC removal or patient transfer out of the ICU. |

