5.2 Secondary Objective(s)

The secondary objective of this study is to compare the differences in the following indicators between the test and control groups:

- Number of positive cases per 1,000 catheter-days of bacterial colonization at CVC tips
- Bacterial colonization rate at the tip of other types of (percutaneous) deep vein catheters and the catheterization site (number of culture positive cases/total catheters \times 100% and number of positive cases per 1,000 catheter-days), including hemodialysis, PICCO, float catheters, etc.

- Incidence rate of Central Line Associated Bloodstream Infections (CLABSI) or Catheter Related Blood Stream Infections (CRBSI)
- Type of pathogenic microorganism (G+/G-/fungal or specific species, drug-resistant bacteria, etc.) and percentage of positivity
- Securement performance of the dressing: Frequency of dressing changes associated with wear time and lift or drop-off
- Effects on the skin of the covered area, e.g. local infection, local skin irritation.

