10.2.4 End-of-treatment Visit

Visit following the completion of dressing securement at the insertion site after removal of DVC. A patient who has multiple catheters withdrawn during the trial should be documented sequentially, but the trial is not to be considered complete at least until the CVC is removed. If replacement of the same type of DVC is performed, only the first removal is recorded and the subsequent replacement is not included in the test or observation.

The following procedures will be completed during the end-of-treatment visit:

1. Assessment of dressing securement performance;
2. Assessment of skin conditions around the catheter site, with reference to the standards for evaluating local skin irritation as listed in the appendix;
3. Photographic documentation of any anomalies;
4. Following departmental routine practice, the tip is cut with sterile scissors after removal, while skin sampling around the insertion site is performed. The samples taken are, under aseptic conditions, sent for pathogenic bacteria testing and species analysis.
5. In case of suspected CLABSI/CRBSI occurrence, sampling and quantitative culture for both catheter and peripheral blood will be performed simultaneously, as well as analysis of pathogenic bacteria species, according to diagnostic evaluation criteria.

The following data will be collected during the end-of-treatment visit:

1. Vital signs: Pulse, blood pressure, respiratory rate, body temperature;
2. Relevant laboratory tests, including blood routine examination: Red blood cell (RBC) count, white blood cell (WBC) count, neutrophil ratio, hemoglobin, platelets, C-reactive protein, etc.;
3. Documentation of dressing securement performance;
4. Documentation of skin conditions around the catheter site, including erythema, edema, rash, etc., and scoring with reference to the standards for evaluating local skin irritation as listed in the appendix.

5. Total duration of DVC placement and duration of application of the test/control dressing;
6. Catheter-tip culture and classification of colonies;
7. Culture and classification of colonies from the skin samples around the insertion site;
8. Any changes in medication use relevant to the trial, including mainly fat emulsions, heparin, blood transfusions and antimicrobial drugs;
9. Confirmation of CLABSI/CRBSI diagnosis;
10. Adverse events, device defects, complaints.

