10.3 Schedule of Events

A schedule of events is in the table below:

Table 10.3-1: Schedule

| Process | Screening and enrollment Day 0 | Dressing change visits | End-of-treatment visit ¹ | Withdrawal or discontinuance of visits ² |
|---|--------------------------------|------------------------|-------------------------------------|---|
| Informed consent collection | X | | | |
| Assessment of inclusion/exclusion criteria | X | | | |
| Randomization | X | | | |
| Demographic data ^a | X | | | |
| Previous medical history | X | | | |
| Vital signs ^b | X | | X | X |
| Routine blood examination ^c | X | | X | X |
| Record of deep vein catheterization | X | | X | X |
| Skin assessment around the catheter site | X | X | X | X |
| Dressing application or change (multiple times) | X | X | | |
| Documentation of relevant concomitant medication | X | X | X | X |
| Evaluation of subject product (dressing edge curling, etc.) | | X | X | X |

| | | | | |
|---|---|---|---|---|
| Total duration of catheterization | | | X | |
| Total duration of test/control dressing use | | | X | |
| Catheter-tip bacterial culture | | | X | |
| Bacterial culture from skin samples around the insertion site | | | X | |
| Blood bacteriological culture | | | X | |
| AE/SAE | X | X | X | X |
| Device defects | X | X | X | X |

Note:

- a: Date of birth, gender, ethnicity, height, weight, etc.;
 - b: Pulse, blood pressure, respiration, temperature;
 - c: Red blood cell (RBC) count, white blood cell (WBC) count, neutrophil ratio, hemoglobin, platelets, C-reactive protein, etc.;
- 1: There may be multiple visits documented when multiple deep vein catheters are removed in succession;
 2. For subjects withdrawing from or discontinuing the trial.

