11.4 Safety and Event Sponsor Reporting Requirements

This study requires that the following events be reported to the Sponsor, in addition, to completing Case Report Form:

- Reportable Adverse Device Effects, as described in Section 3.3.2
- Any Adverse Events deemed by the Investigator to be related to participation in the study and considered to be due to the study intervention or comparator product.
- All Unanticipated Adverse Device Effects
- All Serious Adverse Events, Serious Adverse Device Effects, Unanticipated Serious Adverse Device Effects
- Device Deficiencies
Devices meeting the performance expectations but not exceeding performance expectations will NOT be captured as device deficiencies.
- Any Complaint related to any 3M commercially available product used in the study.

The Investigator shall report information relating to the event, and include dates of the event, severity rating, treatment, seriousness and relationship to the investigational device.

Any Adverse Events, which are not safety related, which are ongoing at the end of the study should be marked as “*persistent*” per study specific CRF. Any Events which related to safety OR are persistent and deemed related to the study device, may be followed for an additional 30 calendar days. Events reported by subjects after the last study visit may be reported to the Sponsor up to 30 calendar days from the date of the last visit.

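### CLABSI is defined to include infections up to 48 hours after catheter removal, but neither document requires anyone to look for them over those 48 hours

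*Protocol*

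**What the plan says.** **Definition.** Protocol Appendix B extends CLABSI beyond the period of catheter use to infections arising "within 48 hours after removal of indwelling central venous catheters". It limits the term to primary bloodstream infections in hospitalized patients. Its CRBSI definition has no such time clause.

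**Use.** Protocol 5.2 makes the incidence of CLABSI or CRBSI a secondary objective to be compared between groups. Protocol 19.4 (for catheter-related bloodstream infection) and SAP 6.3.2 (for suspected CLABSI/CRBSI) test it by chi-square or Fisher's exact test. SAP 6.4 also tabulates CLABSI and CRBSI as treatment-emergent adverse events.

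**Observation.** The Synopsis (Design) has the investigator monitor subjects "until the end of the trial, i.e. CVC removal or patient transfer out of the ICU". Protocol 10.2.4 describes the end-of-treatment visit as a "Visit following the completion of dressing securement at the insertion site after removal of DVC" and gives no interval after removal. It adds that "the trial is not to be considered complete at least until the CVC is removed". The data items for that visit include "Confirmation of CLABSI/CRBSI diagnosis". The schedules in Protocol 10.3 and SAP 3.4 mark blood culture at that visit only and have no later column for subjects who complete.

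**After the last visit.** Protocol 11.4 allows certain safety-related or device-related events to be followed for a further 30 days, and says that "Events reported by subjects after the last study visit may be reported to the Sponsor up to 30 calendar days". Protocol 11.4.1 requires SAEs to reach the sponsor within 24 hours of staff becoming aware of them.

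**The concern.** The endpoint has a time window, and the plan does not say that the last part of that window will be observed. A subject whose CVC is removed and whose end-of-treatment visit is completed the same day can develop a bloodstream infection the next day that meets the CLABSI definition. No planned procedure would find it.

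A CLABSI rate that does not match its definition is at stake. Reducing catheter-related bloodstream infection is part of the product's stated indication (Protocol 2.0), so this secondary result will be read closely. Because the time of the visit is not fixed, the length of post-removal observation can also vary from subject to subject. The trial is open-label, so whatever is picked up through optional reporting could in principle depend on the arm.

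**Working it through.** **1. Definition against observation**

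| Element | Where | What it gives |
|---|---|---|
| CLABSI window | Appendix B | catheter use plus 48 h after removal |
| End of trial | Synopsis (Design) | CVC removal or ICU transfer |
| Last scheduled contact | Protocol 10.2.4 | visit after removal, no interval stated |
| CLABSI/CRBSI confirmation | Protocol 10.2.4 | at that visit |
| Blood culture | Protocol 10.3, SAP 3.4 | at that visit only |
| CVC still in place on leaving the ICU | Protocol 9.2 | lost to follow-up |
| Study time in the analysis | SAP 6.2.3.1 | stops at completion or withdrawal |
| 48-hour rule in the SAP | SAP 4.1.2, 6.3.2, 6.4 | none |
| After the last visit | Protocol 11.4, 11.4.1 | optional 30-day follow-up or reporting; SAE reporting on awareness |

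No row requires CLABSI status to be established through 48 hours after removal.

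**2. How much of the window is unobserved, at most**

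Inputs: a post-removal window of 48 h = 2 days (Appendix B) and participation of about 3 to 14 days (Protocol 6.0). The 7-day value is an intermediate point and the maximum dressing wear in Protocol 10.2.3. Let d be the days observed from enrollment to removal, and suppose observation stops exactly at removal. Then

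unobserved share of the post-enrollment window = 2 / (d + 2)

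- d = 3: 2/5 = 40%
- d = 7: 2/9 = 22%
- d = 14: 2/16 = 12.5%

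These are upper limits, for two reasons. If the visit takes place t hours after removal (t up to 48), the numerator falls to 2 − t/24. And d is study participation, not catheter dwell. SAP 6.2.2 computes a baseline insertion duration, so a catheter can have been in place before randomization. With k days of earlier dwell, the share of the whole at-risk period is 2 / (k + d + 2), which is smaller.

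The figures are shares of time. The documents give no infection rate for the 48 hours after removal, so they do not convert into a share of CLABSI cases missed.

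**3. What one missed case would weigh (illustration)**

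The protocol gives no expected CLABSI rate. Its background (Protocol 2.0) cites CRBSI in about 3–5% of catheterizations. Assume, for scale only, that CLABSI counts were of that order. With 220 per group:

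- 220 × 0.03 = 6.6 events; one missed is 1/6.6 = 15%
- 220 × 0.05 = 11 events; one missed is 1/11 = 9%

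CRBSI is not CLABSI, and EC-3 and EC-7 exclude patients judged at high risk, so the true count may be lower. Each missed case would then weigh more.

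**4. What is not touched**

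The tip and the skin are sampled at removal, so the primary endpoint does not depend on the 48 hours. The sample size of 220 per group is set on tip colonization, and no power is stated for CLABSI/CRBSI.

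**The case against.** The strongest reply is that observation does not simply stop at removal, and much of it stands. Protocol 10.2.4 makes CVC removal the earliest point of completion, not a fixed end. The same visit collects tip and skin culture results, which cannot exist at the moment of removal, so data entry must run on afterwards. Subjects with several catheters have successive end-of-treatment visits that may cover part of the window. But nothing requires the visit to reach 48 hours, its sampling ties it to removal, and only the CVC is mandatory (IC-4). Later entry of culture results is also not the same as looking for new infections.

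Four stronger readings are tempting, and the documents do not support them:

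- *Subjects' own reports are the only later route.* Protocol 11.4 also permits 30-day follow-up that does not depend on the subject. A serious bloodstream infection would be reportable as an SAE once staff knew of it, with no stated cut-off at the last visit. These routes can catch cases. The first is optional, and the second is a reporting deadline rather than surveillance. SAP 6.4 draws on adverse events but bases its analysis on the treatment period, so it is not clear that a post-removal case would be counted.
- *The infection rate as a whole is understated.* The 48-hour clause belongs to CLABSI, not CRBSI. Under-counting is possible, not demonstrated.
- *Up to 40% of CLABSIs are lost.* That is the extreme share of time, under the shortest participation and no observation after removal.
- *The comparison is biased.* The same gap applies to both arms. A difference by arm is a risk of optional reporting in an open-label trial, and nothing shows that it would occur.

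It may also be said that this is one of several secondary outcomes with no stated power. That limits the seriousness but does not remove the mismatch.

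**Conclusion.** The plan defines CLABSI over a window that it does not require anyone to observe in full. Followed as written, it may under-count CLABSI in a compared secondary endpoint and in the matching adverse event tables. Where CLABSI and CRBSI are reported together, the combined figure is affected through its CLABSI part.

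The size is unknown. The unobserved part is at most 12.5% to 40% of post-enrollment time at risk over the stated 3 to 14 days, assuming that observation stops at removal. How many events fall in that time cannot be derived from the documents. The main expected effect is a lower count and less precision in both arms.

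This does not threaten the primary conclusion. It is worth correcting because the remedy is cheap and the result would otherwise not match its label.

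**What to change.** **Preferred.** Add to Protocol 10.2.4 and to both schedules a check of hospital information system and laboratory blood-culture records covering the 48 hours after CVC removal. It should:

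- apply to all subjects while they remain hospitalized, including those moved out of the ICU after removal;
- assign CLABSI status by time of onset or specimen collection within 48 hours, and finalise it only when those cultures have resulted, so that cultures pending at 48 hours are counted;
- record discharge or death before 48 hours as incomplete observation, not as absence of CLABSI.

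SAP 6.3.2 and 6.4 should then use the same window.

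**Otherwise.** Restate the endpoint as CLABSI observed up to the end-of-treatment visit, and give that visit a stated time after removal. This needs no new data, but the rate then no longer matches the Appendix B definition.

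Either way, the Synopsis (Design), Protocol 10.2.4, 10.3 and 11.4 and Appendix B must be reconciled.

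**Cost.** One CRF field and a short chart check per subject, at a single hospital whose information system is already a data source (Protocol 10.2.2). The record check itself adds no visit and no sampling.
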